6.5.2 Adverse Events

All adverse events (AEs) will be documented from the date of randomization until study exit. For patients who permanently discontinue sorafenib in either arm of the study, AEs will be documented for 30 days from the date of discontinuation. After this period, only AEs considered to be related to TheraSphere will be collected.

A treatment emergent AE (TEAE) is defined as an event that was not present at baseline or worsened in severity following the start of treatment through to 30 days after the end of the last study treatment (sorafenib and/or TheraSphere) initiated prior to progression

date by investigator assessment, or start date of subsequent HCC therapy, whichever comes first.

The start of treatment will be defined as the start date of sorafenib and the date of first angiogram, prior to progression date by investigator assessment, whichever occurs first. The last study treatment will be sorafenib for patients who received only sorafenib or both sorafenib and TheraSphere prior to progression, and will be TheraSphere for patients who only received TheraSphere prior to progression. Partial AE start and stop dates will be imputed as described in Section 6.2.1.3.

The investigator's verbatim term of an AE will be mapped to a system organ class and preferred term using the MedDRA Version 14.0 dictionary (Medical Dictionary for Regulatory Activities). The investigator will use the NCI Common Toxicity Criteria for Adverse Events [CTCAE] (version 4.0) or the protocol specific criteria when no NCI CTC criteria are available for the AE to determine the severity of the AE.

Adverse events related to sorafenib, device, and angiographic procedures are defined as those events recorded on the eCRF with relationship of possibly, probably, or definitely relationship. Relation to TheraSphere (device) is not appropriate for the Control group.

The incidence of TEAEs will be the number of patients who had the AE (counted only once) divided by the number of patients in the safety population and represented as a percentage. For subgroup summaries of AEs, the percentage will be represented as the number of patients with the AE event divided by the number of patients of that group in the safety population. The incidence of AEs will be the number of times an event occurs, counting worsening events only once. For worsening events, the AE end date of the earlier AE will be the same as the start date of the same AE with a higher severity.

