8.3 Analysis Populations

8.3.1 *Modified Intent-to-Treat (mITT) Population*

All randomized patients who met the study eligibility criteria at randomization will form the modified Intent-to-Treat (mITT) Population and will be analyzed according to the treatment group to which they were randomized. This population will be used to analyze all efficacy endpoints.

8.3.2 *Safety Analysis (SA) Population*

All randomized patients who received study treatments at least once, prior to progression (i.e. prior to date of progression) as assessed by investigator according to RECIST 1.1, will form the Safety Population and will be analyzed according to the treatment actually

received prior to progression. Note that patients who received only TheraSphere (no sorafenib) prior to progression do not receive full treatment of either protocol-defined treatment group, so will be analyzed as a separate group in the safety population. This population will be used in all safety reporting and analysis.

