8.3.3 Per Protocol (PP) Population

The Per Protocol population is the subset of the mITT population excluding patients with major protocol deviations which may affect the efficacy evaluation. Patients in the PP population will be analyzed according to the treatment group to which they were randomized.

Major protocol deviations resulting in a patient being excluded from the PP population will include, but may not be limited to, the following:

- Baseline imaging assessment not performed
- Baseline imaging assessment performed >42 days prior to date of randomization (note that although the screening period for baseline imaging assessment was 28 days, an additional 14-day window is being applied so that only baseline imaging assessments >42 days before randomization will be deemed to be a major protocol deviation that may affect the efficacy evaluation)
- Post-randomization imaging assessments not performed for 3 consecutively planned timepoints (i.e. the number of days between imaging assessments is >224 days), defined as
 - the first post-randomization imaging assessment, prior to progression (i.e. prior to date of progression) as assessed by investigator according to RECIST 1.1, occurs at >32 weeks (i.e. >224 days) after randomization, or
 - any post-randomization imaging assessment, prior to progression as assessed by investigator according to RECIST 1.1, occurs at >32 weeks (i.e. >224 days) after the previous post-randomization imaging assessment
- Randomized study treatment not received (TheraSphere and/or sorafenib) prior to progression as assessed by investigator according to RECIST 1.1
- Y90 (including TheraSphere) received by patients in the control arm prior to progression assessed by investigator according to RECIST 1.1
- TheraSphere dose absorbed by perfused volume (as defined in Section 6.5.1.1) lower than the protocol stated range of 120 Gy – 10% (i.e. <108 Gy) prior to progression as assessed by investigator according to RECIST 1.1
- Bilobar disease at baseline (as defined in Section 6.5.1.1) but only one lobe treated with TheraSphere prior to progression assessed by investigator according to RECIST 1.1
- For patients enrolled under all protocol versions implemented:
 - For the control arm:
 - Start of sorafenib >28 days after randomization

- o For the treatment arm:
 - First administration of TheraSphere prior to progression >35 days after randomization, or

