11.4 APPENDIX 4: Definition and Derivation of Subsequent HCC Therapy

A patient is considered to have received ‘subsequent HCC therapy’, after the protocol required treatments, if they had

- a subsequent systemic anti-cancer treatment (excluding sorafenib), and/or
- a non-protocol liver directed therapy (excluding ablation/surgery)

Subsequent systemic anti-cancer treatment will be identified using all non-sorafenib records from the “Best Available Care - Post Treatment Discontinuation – Medication” eCRF page. Note that all records on the “Best Available Care - Post Treatment Discontinuation – Medication” eCRF page are expected to be systemic anti-cancer treatments for HCC after data cleaning has been completed.

Non-protocol liver directed therapy will be identified using all records (except ablation/surgery) from “Additional Procedures” eCRF page. This eCRF page captures any procedures relating to liver directed therapies outside the study protocol, such as liver ablation, liver surgery, liver external beam radiation therapy, SIRT with rhenium, SIRT with Y90 (including TheraSphere for patients randomized to control group), TACE, and transarterial embolization (TAE). The free text field “procedure term” will be reviewed and categorized by physician, which will be finalized prior to the database hard lock. Procedures identified as liver ablation and liver surgery by physician’s review will not be considered as subsequent HCC therapy.

Notes:

- Treatments recorded on the “Resection / HCC Stage Migration” eCRF page will not be considered as subsequent HCC therapy, since these treatments are delivered to patients who had a downstaging of disease and represents a population possible to have better outcomes and important to follow-up.
- TheraSphere treatment/retreatment for patients randomized to TheraSphere group, recorded on the “TheraSphere Doses Administered” eCRF page, are study treatment per protocol, so will not be considered as subsequent HCC therapy.

[figure not shown]
**11.5 APPENDIX 5: Statistical Details of the Adaptive Design for Protocol TS-103
STOP-HCC**

Statistical Details of the Adaptive Design

1 Design Overview

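### Patients with a study angiogram but no TheraSphere or sorafenib before progression fall outside every adverse-event summary, and the SAP leaves open the safety column for control patients given TheraSphere

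*SAP*

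**What the plan says.** **Who is counted.** SAP 8.3.2 admits "All randomized patients who received study treatments at least once, prior to progression". These patients "will form the Safety Population and will be analyzed according to the treatment actually" received before progression, and patients with TheraSphere but no sorafenib form a separate group. On scope, the section says "This population will be used in all safety reporting and analysis", and 8.7 repeats the rule. SAP 6.5.2 glosses study treatment as sorafenib and/or TheraSphere. The treated categories in 8.1 are sorafenib only, both, and TheraSphere only.

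**When events count.** SAP 6.5.2 says: "The start of treatment will be defined as the start date of sorafenib and the date of first angiogram", taking whichever is earlier and requiring it to precede progression. The window ends 30 days after the last study treatment begun before progression "or start date of subsequent HCC therapy, whichever comes first". SAP 6.5.2 also plans, for the Treatment group, a separate display of TEAEs between the angiogram and the start of sorafenib. SAP 8.7.2 plans a summary of TEAEs attributed to the angiographic procedure.

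**Control patients given TheraSphere.** SAP 8.3.3 foresees them, listing "Y90 (including TheraSphere) received by patients in the control arm prior to progression" as a reason for exclusion from the Per Protocol population. Appendix 4 (SAP 11.4) includes "SIRT with Y90 (including TheraSphere for patients randomized to control group" among the procedures outside the protocol that count as subsequent HCC therapy. It treats TheraSphere in the TheraSphere arm as study treatment. SAP 5.2.5 derives the Safety Population only from study treatments received before progression.

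**The concern.** The window for counting events and the population in which they are counted start from different acts. The plan regards harm from work-up as relevant: it starts the clock at the angiogram and reserves a summary for angiographic events. It then requires a later step, an actual dose of TheraSphere or sorafenib, before a patient can appear in that summary.

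The omission is selective. The patients dropped are those whose course after work-up was bad enough, for whatever reason, that neither treatment was given before progression. If a work-up complication was the reason, the event most worth reporting is the one left out of the rate.

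The second issue is one of classification. For a control patient given TheraSphere before progression, one section can be read as making TheraSphere part of the treatment received, while another makes it the event that ends safety observation. Two programmers could build different safety tables from the same text.

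**Working it through.** The SAP gives no figure to reproduce, so the check is to apply SAP 5.2.5, 5.2.6, 6.5.2, 8.1, 8.3.2, 8.7 and Appendix 4 to each type of patient.

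| Patient | TEAE window | Safety Population and column |
|---|---|---|
| A. TheraSphere arm: angiogram, then neither treatment before progression | Opens at the angiogram; no last study treatment from which to count 30 days | Not in the population; no AE column |
| B. TheraSphere arm: angiogram, then sorafenib only before progression | Opens at the angiogram; ends 30 days after sorafenib or at subsequent HCC therapy | In; sorafenib only |
| C. Control: sorafenib, then TheraSphere before progression | Opens at the earlier of sorafenib start and first angiogram; closes on the TheraSphere date | In; TheraSphere and sorafenib, or sorafenib only, depending on the reading |
| D. Control: TheraSphere only before progression | First angiogram to the TheraSphere date | TheraSphere-only group on one reading; outside the population on the other |

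**Type A** is the gap. The window opens but the patient is not admitted. The missing end date also matters for the rates per 100 patient-years in 8.7.2, whose denominator is time at risk for TEAEs: even if type A patients were admitted, that time could not be computed unless subsequent HCC therapy happened to close the window.

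**Type B** bounds the gap. Protocol 9.2.15.1.1 lets a patient found unsuitable for TheraSphere go on to sorafenib. If sorafenib starts before progression, the patient is in the population with work-up events counted.

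**Type C**, with days assumed for illustration: sorafenib on days 8–200, TheraSphere on day 100, progression on day 220.
- Without the Appendix 4 cut, the window is day 8 to day 200 + 30 = 230, which is 230 − 8 + 1 = 223 days.
- With the cut, it is day 8 to day 100, which is 100 − 8 + 1 = 93 days.
- The 223 − 93 = 130 days after TheraSphere are not counted. The 93 days before it, up to and including that day, are.

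**Size, on assumed proportions only.**
- Angiogram only: 520 planned patients at 1:1 give about 260 per arm. 0.02 × 260 = 5.2 and 0.05 × 260 = 13, so 5–13 patients.
- Control patients given TheraSphere, on the reading that moves them to a TheraSphere column: 1–10 in an assumed column of 200 is 1/200 = 0.5% to 10/200 = 5% of the denominator. If they add no device events, an assumed true rate of 10% would show as at worst 10% × (1 − 0.05) = 9.5%.

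**The case against.** **On angiogram-only patients.** Requiring at least one study treatment is the protocol's own definition (10.2.1), so the SAP is not inventing an exclusion. The patients are not invisible either. SAP 7.1 lists all eCRF data by patient. SAP 8.7.2 lists all AEs, serious AEs and fatal AEs. SAP 6.5.1.1 summarises reasons for not receiving TheraSphere. SAP 8.1 counts untreated patients who discontinue. Deaths of eligible patients enter overall survival on the mITT population, and the IDMC reviews safety events during the trial. All of this stands, and it rules out saying that these events vanish from the safety results. It does not close the gap: a listing does not correct a rate, and the protocol's definition was not paired with a window that opens at the angiogram.

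**On control patients given TheraSphere.** A reader might infer that they enter the TheraSphere column with their window already closed and so dilute device-event rates. The documents do not support that as a statement of what the plan does:
- The plain wording of 8.3.2 allows the move. But 5.2.5 restricts the derivation to study treatments, and Appendix 4 puts control-arm TheraSphere outside the protocol. On that reading a patient who took sorafenib first stays in the sorafenib column, and closing the window there fits the aim in 5.2.6 of keeping subsequent therapy out of the AE profile.
- The window is not already closed, because events up to the TheraSphere date count.
- There is no single TheraSphere column, since TheraSphere-only patients are separate.
- The SAP rule "Relation to TheraSphere (device) is not appropriate for the Control group" follows the causality instruction to investigators in Protocol 12.2.1. Rewording the SAP cannot recover attributions that investigators were told not to make.

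These objections stand. What is left is an ambiguity to settle, not a shown dilution.

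**Conclusion.** The first part holds on the text. TheraSphere-arm patients with a study angiogram and neither treatment before progression are in no AE summary, including the one planned for angiographic events, and their window has no defined 30-day end. This does not reach patients who go on to sorafenib before progression, and it concerns summarised rates, not listings.

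The second part holds only as an ambiguity. The SAP does not say which column a control patient given TheraSphere before progression enters. If it is a TheraSphere column, that patient brings events up to the TheraSphere date and none after it.

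The documents give no number of affected patients, so the 5–13 and the 0.5–5% above rest wholly on assumed proportions and column size, and the latter on one of two readings. No inference on AEs is planned (8.7.2), and neither issue touches the efficacy analyses or alpha. The matter is the completeness and reproducibility of the safety tables.

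**What to change.** 1. **SAP 8.3.2:** also admit TheraSphere-arm patients who had the first study angiogram before progression. Show those with neither treatment before progression as a separate angiogram-only column, with a matching category in 8.1.
2. **SAP 6.5.2, and 5.2.6 to match:** for that column, end the TEAE window 30 days after the last angiographic procedure or at the start of subsequent HCC therapy, whichever is earlier.
3. **SAP 5.2.5:** declare the departure from the protocol's safety definition.
4. **SAP 8.3.2, control patients:** assign the column by treatment received before the earlier of progression and start of subsequent HCC therapy, so that column and window rest on one classification. A control patient who took sorafenib first then stays in the sorafenib column. One with no sorafenib before TheraSphere would be in no column, which is why step 5 is needed.
5. **SAP 8.7.2:** add a listing of AEs after TheraSphere in control patients.

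The cost is SAP wording, one extra column and one extra listing. AEs are recorded from randomization, so most of the data already exist; collection after sorafenib stops is limited, and device attribution in control patients cannot be recovered. The downside is a Safety Population slightly larger than the protocol's wording gives.

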Treatment Group (TheraSphere followed by Sorafenib)	
As soon as possible after randomization, hepatic angiography will be performed to assess hepatic vascular anatomy and tumor hypervascularity, followed by a ^{99m}Tc-MAA scan to rule-out gastrointestinal flow or unacceptable lung shunting. Embolization may be performed, if necessary, to close off gastrointestinal flow so that the patient can qualify for treatment with TheraSphere. The lobe with the highest tumor burden should be scheduled for first treatment with TheraSphere.
 
Patients will not be able to receive TheraSphere if the potential radiation dose to the lungs exceeds 30 Gy for a single treatment or cumulative 50 Gy or embolization cannot be performed to effectively block GI blood flow from the hepatic arterial system. If radiation exposure to the lungs exceeds 30 Gy (or 50 Gy cumulative), dose reduction of TheraSphere is permitted (minimum dose allowed is 90 Gy ± 10%).
 
If after consideration of dose reduction, radiation exposure to the lung continues to be greater than 30 Gy (or 50 Gy cumulative), sorafenib treatment will be initiated as soon as possible and ^{99m}Tc-MAA will be repeated after 4 weeks of continuous treatment with sorafenib. If radiation exposure to the lung is less than 30Gy for a single treatment or 50Gy cumulative within a target dose of 90-120 Gy +10% , the patient may commence treatment with TheraSphere. In such instances, sorafenib should be discontinued at least 7 days prior to the administration of TheraSphere and resume sorafenib at least 2 weeks after the administration of TheraSphere. If radiation exposure to the lung is outside of the permitted range, treatment with sorafenib should be continued.
 
In the case where TheraSphere could not be delivered at target dose of 120 Gy ± 10% within 28 days of randomization, these patients will be included in the Treatment Group Intent-to-Treat analysis, but not in the Treatment Group Per-Protocol analysis.
 
TheraSphere Treatment #1: TheraSphere treatment should occur within 28 days of randomization, and prior to the initiation of sorafenib. The number of infusions required to achieve lobar treatment will be determined by the Investigator, based on the hepatic vascular anatomy.
 
Patients will receive 120 Gy ± 10% of TheraSphere to the treated lobe of the liver and may be administered in multiple infusions to address vascular abnormalities.
 
TheraSphere Treatment #2: Patients who have bilobar disease at randomization should have TheraSphere administered to the untreated lobe. If needed, a second angiogram and/or ^{99m}Tc-MAA scan should be performed. Such treatments typically take place 28 days after the treatment to the first lobe.
 
From 2 to 6 weeks following TheraSphere treatment of all treatable liver tumors observed at the time of randomization, patients should initiate standard-of-care sorafenib treatment in accordance with the sorafenib label directions.
 
Re-treatment of the same patient with further cycles of TheraSphere is permitted if a

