9.2.15 STUDY TREATMENTS

9.2.15.1 THERASPHERE

TheraSphere will be administered to the diseased lobes present at randomization, before initiation of the SOC sorafenib treatment. Patients with unilobar disease will receive treatment of the diseased lobe. Patients with bilobar disease will have the second procedure visit such that the second administration occurs within Weeks 5-8 following randomization.

SOC Sorafenib will be prescribed in accordance with the sorafenib package insert. To minimize the risk of additive or synergistic adverse events, sorafenib and TheraSphere should not be administered concurrently. SOC sorafenib treatment will be initiated at least two (2) weeks after the administration of TheraSphere is completed. Generally, patients should initiate SOC sorafenib between 2 and 6 weeks after TheraSphere has been administered to all disease present at randomization.

Safety Risks will be minimized by treating all liver tumors present at randomization with TheraSphere followed by an interval of at least 2 weeks prior to initiating sorafenib therapy to allow decay of the radioactive microspheres and recovery from the expected transient adverse effects (fatigue, abdominal pain, nausea/vomiting) associated with TheraSphere administration. Ideally, SOC sorafenib should be started no later than 6 weeks following TheraSphere treatment.

During follow-up, for patients in the Treatment group who have demonstrated hepatic progression with hepatic lesions amenable to TheraSphere, re-treatment with TheraSphere is allowed. Sorafenib will be discontinued seven (7) days prior to TheraSphere treatment (equivalent to approximately five to seven half-lives) through 2 weeks after TheraSphere treatment to permit radioactive decay and patient recovery from transient side effects.

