9.2.15.1.1 THERASPHERE PRE-TREATMENT EVALUATION

Patients randomized to the Treatment group must undergo the following evaluations to determine eligibility to receive the TheraSphere. These are described in detail in Appendix 2, pages 1254-1255 and include:

- Hepatic Angiography: selective celiac and superior mesenteric arteriograms are needed to evaluate the hepatic arterial anatomy for the whole liver, as well as evaluation of potential sources of extra-hepatic blood supply to tumors. The goal is to identify, within the hepatic vascular anatomy, a catheter placement location that allows a single TS infusion throughout the lobar tumor volume without administration of microspheres to extra-hepatic structures.
- A technetium-99m macroaggregated albumin (^{99m}Tc -MAA) scan is used to assess the potential for shunting microspheres to the lungs as well as the potential for the deposition of microspheres to the gastrointestinal (GI) tract. Repeat ^{99m}Tc -MAA may be needed for subsequent treatments to estimate cumulative lung shunt or re-asses GI flow. Note that 3 technical factors, as discussed in Appendix 2 (time between administration of ^{99m}Tc -MAA and the scan, ^{99m}Tc -MAA particle size and the presence of free ^{99m}Tc -MAA) can lead to an over-estimation of shunting to the lungs and should be controlled.

TheraSphere should not be administered to a patient randomized to the Treatment group if:

- Deposition of microspheres to the GI tract that cannot be corrected by placement of the catheter distal to collateral vessels or the application of standard angiographic techniques, such as coil embolization to prevent deposition of microspheres in the GI tract.
- Exposure of radiation to the lungs of 30 Gray (Gy) for a single infusion or a cumulative 50 Gy limit for all infusions of TheraSphere - estimated during TheraSphere dose calculation as described in Section 9.2.15.1.3

In the event that the patient is determined not to be suitable and/or cannot be safely treated with TheraSphere, that patient may proceed to treatment with the planned SOC sorafenib regimen as described in Section 9.2.15.2.

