8.7.2 Adverse Events

The investigator's verbatim term of each AE will be mapped to system organ class and preferred term using the MedDRA Version 14.0 dictionary.

Adverse events will be summarized by system organ class and preferred term; a patient will only be counted once per system organ class and once per preferred term within a treatment. Patient counts and percentages and event counts will be presented for each treatment group for the following summaries:

1. Overall summary of TEAEs
2. All TEAEs (also presented by preferred term only in descending order).
3. All TEAEs with CTCAE grade ≥ 3 (also presented by preferred term only in descending order).
4. All TEAEs considered related to sorafenib.
5. All TEAEs considered related to device (ADE).
6. All CTCAE grade ≥ 3 TEAEs considered related to device.
7. All TEAEs related to angiographic procedure.
8. All TEAEs with fatal outcome.
9. All treatment emergent serious adverse events (SAE).
10. All treatment emergent serious adverse device events (SADE)
11. All TEAEs leading to sorafenib discontinuation
12. All TEAEs of special interest (presented by AESI category and preferred term)
13. All TEAEs of special interest with CTCAE grade ≥ 3 (presented by AESI category and preferred term)

Event rate (per 100 patient years) will also be presented by treatment group for each of the above TEAE categories. For each category, the event rate is defined as the number of patients with TEAEs in that category divided by the total duration of patients at risk for TEAEs and then multiplied by 365.25×100 to present in terms of per 100 patient years.

For the summary of TEAEs by CTCAE grade, if a patient has multiple events occurring in the same body system or same preferred term, then the event with the highest CTCAE grade will be counted. For TEAEs by relationship to study device, if a patient has multiple events occurring in the same body system or same preferred term, the event with the highest association to study device will be summarized (unknown is considered a higher association to study device than not related, but less of a relationship than possibly, probably, and definitely). Adverse events related to sorafenib, device and angiographic procedure are defined as a subset of AEs with a relationship of either possibly, probably, definitely, or unknown.

No statistical inference between the treatments will be performed on AEs.

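### The fatal TEAE rate per 100 patient-years in the TheraSphere-plus-sorafenib safety column is biased low: members must survive to receive both treatments, but their time at risk starts at first angiogram

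*SAP*

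**What the plan says.** **Column membership.** SAP 8.3.2 analyses safety patients by the treatment actually received before investigator-assessed progression, for all safety reporting. Patients who had only TheraSphere by then "do not receive full treatment of either protocol-defined treatment group, so will be analyzed as a separate group in the safety population". This leaves three columns: sorafenib, TheraSphere plus sorafenib, and TheraSphere only.

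**Clock.** SAP 6.5.2 states: "The start of treatment will be defined as the start date of sorafenib and the date of first angiogram", whichever is earlier. The window runs "through to 30 days after the end of the last study treatment" begun before progression, or to subsequent HCC therapy if that comes first.

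**Rate.** SAP 8.7.2 defines the event rate as "the number of patients with TEAEs in that category divided by the total duration of patients at risk for TEAEs", scaled to 100 patient-years. It is shown by treatment group for each listed category, and fatal TEAEs are one of these.

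**Order of treatment.** In the Protocol synopsis, "TheraSphere treatment should occur within 28 days of randomization, and prior to the initiation of sorafenib". Section 9.2.15.1 adds: "SOC sorafenib treatment will be initiated at least two (2) weeks after the administration of TheraSphere is completed". The usual interval is 2 to 6 weeks after all initial TheraSphere, and the second lobe is typically treated 28 days after the first.

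**Sorafenib-first route.** If the estimated lung dose stays too high after dose reduction, sorafenib is started and the MAA scan repeated after 4 weeks. If TheraSphere then becomes possible, "sorafenib should be discontinued at least 7 days prior to the administration of TheraSphere and resume sorafenib at least 2 weeks after" it.

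**Barred from TheraSphere.** If the work-up shows that TheraSphere cannot be given safely, "that patient may proceed to treatment with the planned SOC sorafenib regimen" (Protocol 9.2.15.1.1).

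**The concern.** A Treatment-group patient who dies after TheraSphere but before sorafenib goes to the TheraSphere-only column. A patient who survives the same weeks brings them into the denominator of the combined column. Those weeks are immortal time: they add patient-years and, by construction, no deaths. A Control patient's clock normally opens on the first day of sorafenib, so the sorafenib column has no matching stretch.

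No between-group test of adverse events is planned, so the displayed rates are themselves the safety comparison. The affected interval is when TheraSphere acts alone. Protocol 5.3 describes hepatic decompensation as a known risk of yttrium-90 microsphere therapy and reports 3% 30-day mortality in one cohort. A fatal rate that reads low here flatters the experimental regimen on the outcome that matters most.

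**Working it through.** The plan states no expected fatal TEAE rate or exposure time, so there is no planned figure to reproduce. Direction follows from the rules; size needs assumptions.

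**1. Direction, by route**

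| Route | Clock opens | Column entered at | Death-free stretch |
|---|---|---|---|
| Usual | First angiogram | First sorafenib | Angiogram to sorafenib |
| Sorafenib first | First angiogram (the lung-dose finding requires the work-up) | First TheraSphere | Angiogram to TheraSphere, including at least 4 weeks on sorafenib |
| Control | Sorafenib | Sorafenib | None |

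Both Treatment-group routes push the combined column's rate down. A sorafenib-first patient who dies before TheraSphere is counted in the sorafenib column.

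There is a further asymmetry. For a TheraSphere-only patient the window closes 30 days after TheraSphere, while sorafenib may start up to 42 days after. A fatal event with onset on days 31 to 42, in a patient who never starts sorafenib, is a TEAE in no column. A survivor's same days still count as time at risk.

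**2. Approximate size**

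With the same constant fatal hazard throughout, gap L weeks and mean sorafenib TEAE window D weeks, displayed rate / true rate ≈ D / (L + D).

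- L, from first TheraSphere: 2 to 6 weeks if unilobar. Adding about 4 weeks between lobes gives 6 to 10 if bilobar. The clock opens at angiogram, which can add 0 to 4 weeks, so up to 14.
- D (assumed): Protocol 5.3 gives a median time to progression on sorafenib of 5.5 months, used here as a stand-in for sorafenib duration. Person-time needs a mean. If exponential, 5.5 / ln 2 = 7.93 months; 7.93 × 30.4375 / 7 = 34.5 weeks. Adding 30 days (4.3 weeks) gives D = 38.8.

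| L (weeks) | D = 12 | D = 38.8 | D = 40 |
|---|---|---|---|
| 2 | 0.857 | 38.8/40.8 = 0.951 | 0.952 |
| 6 | 0.667 | 38.8/44.8 = 0.866 | 0.870 |
| 10 | 0.545 | 38.8/48.8 = 0.795 | 0.800 |

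At D = 38.8 the rate reads about 5% to 20% low. At L = 14 it is 38.8/52.8 = 0.735, about 27% low. Over D = 12 to 40 and L = 2 to 10 the range is about 5% to 45%.

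**3. Simulation of the SAP rules**

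Two million patients per scenario; usual route; TheraSphere 10 days after angiogram; exponential sorafenib duration; median progression 5.5 months; true rate 20 per 100 patient-years in every column.

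| Angiogram to sorafenib / mean sorafenib (weeks) | Combined column | All TheraSphere pooled | Counted from sorafenib start |
|---|---|---|---|
| 4 / 30 | 17.7 | 19.2 | 20.0 |
| 6 / 20 | 15.8 | 18.7 | 20.1 |
| 8 / 20 | 14.8 | 17.5 | 20.1 |
| 12 / 20 | 13.0 | 15.4 | 19.9 |
| 12 / 12 | 11.3 | 14.4 | 20.0 |

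The sorafenib column returned 19.9 to 20.1. The TheraSphere-only column returned 51 to 125. Relative bias was almost the same at true rates of 10 and 40. Pooling alone does not restore the true rate.

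**4. Factors that weaken the bias**

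- TEAEs are placed by onset. A fatal event that starts before sorafenib, with death after sorafenib starts, does count in the combined column. In the 8 / 20 case a mean onset-to-death lag of 14 or 28 days raises 14.8 to 16.0 or 17.0: 20% or 15% low instead of 26%.
- Patients barred from TheraSphere after angiography add some immortal time to the sorafenib column. If 10% of that column (assumed) had a 4-week lead, its rate would fall by about 1% (38.8 / 39.2 = 0.990).

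**5. Simple percentages**

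Let g be the share dying in the gap, q the share alive but never starting sorafenib (assumed to have no fatal TEAE), and p the fatal TEAE share after sorafenib. The combined column shows p; all TheraSphere-treated patients have g + (1 − g − q)p. With g = 3% and p = 10% (both assumed), q = 0 gives 0.03 + 0.97 × 0.10 = 12.7%, and q = 30% gives 0.03 + 0.67 × 0.10 = 9.7%. The direction can go either way.

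**The case against.** **The SAP already splits Treatment-group events into before and after sorafenib start (6.5.2).** If Treatment group there means the randomized arm, early deaths would be tabulated with the arm. The wording allows that reading, although 8.3.2 says its as-treated groups serve all safety reporting. Either way, the split concerns events: it gives no time at risk by period and does not change column membership or the overall rate in 8.7.2.

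**Isolating patients with an incomplete regimen is an open, explained choice, and the tables are descriptive.** This is true, and it limits the consequence. Where counts are not zero, a reader could back-calculate patient-years and pool the columns. But pooling alone still reads low, as the simulation shows.

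**Time at risk is not defined in detail.** Also true. Its start at first angiogram is inferred from the TEAE definition, which is the natural reading.

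**Stronger readings that a reader might infer, and that the documents do not support:**

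- That deaths are hidden. They appear in the TheraSphere-only group, in the by-patient listings and in overall survival, which is compared by randomized arm from randomization.
- That serious or grade ≥3 rates are biased the same way. Non-fatal events before sorafenib stay with patients who later start it, so no direction follows.
- That the fatal percentage is necessarily too low. It can reverse.

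**Conclusion.** The point holds for one displayed quantity: the fatal TEAE rate per patient-year in the TheraSphere-plus-sorafenib column. It is biased low on both routes into that column, and it is not comparable with the sorafenib column's rate. Direction follows from SAP 8.3.2, 6.5.2 and 8.7.2 taken together with the protocol's treatment sequence.

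Size cannot be fixed from the documents. About 5% to 20% low rests on an equal constant hazard, an exponential stand-in for sorafenib duration and gaps of 2 to 10 weeks. Wider assumptions on the window give about 5% to 45%. None of these figures should be read as an estimate of the bias in this trial, and lagged deaths make it smaller. Efficacy analyses are unaffected. The change is worth making because the direction is known, the outcome is death, and the cost is small.

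**What to change.** In SAP 8.3.2 and 8.7.2, keep the planned columns and add one for all patients who received any TheraSphere before progression. For fatal TEAEs, report patient-years and rates by period, with each patient's time assigned to the regimen received so far:

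- **TheraSphere alone:** first TheraSphere to the earliest of sorafenib start, 30 days after the last TheraSphere, or death. Survivors and TheraSphere-only patients then share one window.
- **Both treatments:** from the date both have first been received (sorafenib start on the usual route, first TheraSphere on the sorafenib-first route) to the end of the TEAE window.
- **Sorafenib alone:** include sorafenib-first patients' time from sorafenib start to first TheraSphere.

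Show two sets of events as separate counts so that none are lost: those from angiogram to first treatment, and those more than 30 days after the last TheraSphere but before sorafenib.

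**Cost:** one extra column and extra period denominators. SAP 6.5.1.1 and 6.5.1.2 already derive times to first angiogram, TheraSphere and sorafenib, and SAP 8.1 already counts the three as-treated groups. The drawback is that the pooled column mixes patients with and without sorafenib; the planned columns beside it show that mix.
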